### **5.3. Medical History**

Medical history collected at screening will be coded using the Medical Dictionary for Regulatory Activities (MedDRA) 21.0.

Medical history will be summarized by system organ class (SOC), preferred term (PT), treatment group, and overall. Subjects who report 2 or more medical history items that are coded to the same SOC and/or PT will be counted only once by the unique coded term in the summary.

In addition, numbers and percentages of subjects who have any first degree relatives that had experienced myocardial infarction or stroke before the age of 50 years, experienced myocardial infarction or stroke before the age of 50 years, or have diabetes (type I or II) will be summarized.

The summary will be provided for the Safety Analysis Set. No formal statistical testing is planned.

A by-subject listing of medical history will be provided by subject ID number.

## 6. EFFICACY ANALYSES

### 6.1. General Considerations

The primary analysis set for efficacy analyses will be the FAS, defined in Section 3.1.2.

Efficacy analysis will generally be conducted on the following 2 datasets:

- 1) On-treatment data as specified in Section 3.8.2 with exclusion of the observations described as the following. This is the primary analysis dataset for efficacy analysis.

For subjects who continued study drug BUT did not achieve at least 20% improvement from Baseline in both SJC66 and TJC68 at

- Nominal Week 24 visit, then efficacy data collected after nominal Week 24 visit will be excluded from the primary analysis, OR
- Nominal Week 30 visit if subjects missed Week 24 visit or the response status cannot be determined due to missing SJC66 or TJC68 value at Week 24, then efficacy data collected after nominal Week 30 visit will be excluded from the primary analysis

If subjects missed both visits (Week 24 and Week 30) or the response status cannot be determined at both visits, all the efficacy data collected will be included for analysis.

- 2) All available data (including data collected under standard of care).

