3.2. Study Design

This is a randomized, double-blind, placebo- and active-controlled, Phase 3 study in adult male and female subjects with moderately to severely active RA who have limited or no prior exposure to MTX therapy. The study is designed to evaluate the efficacy, safety and tolerability of filgotinib as well as its effect on patient-reported outcomes, including work productivity, fatigue, and quality of life. In addition, PK will be assessed.

Adult male and female subjects with active RA will be screened to determine eligibility as per the inclusion and exclusion criteria (see Section 4.2 and 4.3, respectively). The Screening period will be up to 28 days. The screening window may be extended to up to 42 days prior to the Day 1 visit for subjects who require repeat collection of radiographs.

Written informed consent must be obtained before any study-related procedures take place. During the Screening period, following signing of the informed consent form (ICF), the subject's radiographs (hands, wrists, and feet) will be sent to central review for confirmation of joint erosion (see inclusion criterion 5; Section 4.2). Note that the subject's radiographs need to be sent to central review as soon as possible after completion and prior to Day 1 to allow for central reading and confirmation of one or more joint erosion in subjects that are seronegative.

Subjects will be randomized in a 2:1:1:2 ratio to filgotinib 200 mg plus MTX, filgotinib 100 mg plus MTX, filgotinib 200 mg alone, or MTX alone for up to 52 weeks in a double-blind fashion.

At Week 24, subjects who have not achieved a 20% improvement from Day 1 in both SJC and TJC will discontinue investigational therapy but will continue with study visits and assessments per protocol. All subjects who discontinue from investigational therapy are to receive standard of care treatment for their RA as determined by the investigator.

Responders at Week 24 will continue on the treatment regimens to which they were randomized through Week 52.

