All subjects will be evaluated for loss of therapeutic response from Week 30 through the Week 52 study visit. Subjects failing to maintain at least a 20% improvement from Day 1 in TJC and SJC (as confirmed at 2 consecutive visits) will discontinue investigational therapy but will continue with study visits and assessments. All subjects who discontinue from investigational therapy are to receive standard of care treatment for their RA as determined by the investigator.

Subjects who have received at least one dose of study drug and choose to prematurely terminate study participation for any reason should complete an ET visit at the time of study discontinuation, as well as a post dosing visit four weeks after the last dose of study drug (post treatment Week 4) regardless of dosing duration.

[figure not shown]
At completion of the 52-week treatment period, subjects (who did not discontinue assigned study drug or have not met criteria for loss of therapeutic response) will be provided the option to enter a Long Term Extension (LTE) study (GS-US-417-0304).

For those subjects not entering the LTE, a follow-up visit will be planned at Post Treatment Week 4.

To enhance the safety monitoring during the study, a DMC consisting of independent experts will be convened to periodically review the accumulating safety data for the study. In addition, a cardiovascular safety endpoint adjudication committee (CV-SEAC) will be convened to periodically review and adjudicate all possible major cardiovascular events (MACE).

The assessments planned to be performed at each visit are detailed in the study procedures table (Appendix 2). A schedule of the study design is provided below.

Figure 3-1. Study Design

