3.5. Criteria for Interruption or Discontinuation of Study Treatment

3.5.1. Study drug interruption considerations:

The Gilead Medical Monitor should be consulted prior to study drug interruption when medically feasible.

Study drug interruption should be considered in the following circumstances; *prior to resumption of study drug, the investigator should discuss the case with the Gilead medical monitor:*

- Intercurrent illness that would, in the judgment of the investigator, affect assessments of clinical status to a significant degree.
- Subject is scheduled for elective or emergency surgery (excluding minor skin procedures under local or no anesthesia); timing of study drug pausing should be determined in consultation with the Gilead medical monitor.
- Any subject who develops a new infection during the study should undergo prompt and complete diagnostic testing appropriate for an immunocompromised individual, and the subject should be closely monitored.

NOTE: During the time of study drug interruption for any of the above, the subject may continue to have study visits and to take part in procedures and assessments, if deemed medically appropriate by the investigator.

3.5.2. Study drug discontinuation considerations:

The Gilead Medical Monitor should be consulted prior to study drug discontinuation when medically feasible.

Study medication should be permanently discontinued in the following instances:

- Any opportunistic infection
- Any **serious** infection that requires antimicrobial therapy or hospitalization, or any infection that meets SAE reporting criteria.
- Complicated herpes zoster infection (with multi-dermatomal, disseminated, ophthalmic, or CNS involvement)
- Evidence of active HCV during the study, as evidenced by HCV RNA positivity
- Evidence of active HBV during the study, as evidenced by HBV DNA positivity
- Unacceptable toxicity, or toxicity that, in the judgment of the investigator, compromises the subject's ability to continue study-specific procedures or is considered to not be in the subject's best interest
- Non-responder at Week 14 OR at 2 consecutive visits after Week 30 as outlined in Section 3.2
- Subject request to discontinue for any reason
- Subject noncompliance
- Pregnancy during the study (Section 7.7.2.1 and Appendix 5)
- Discontinuation of the study at the request of Gilead, a regulatory agency or an institutional review board or independent ethics committee (IRB/IEC)

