**Figure 1-1. Study Design**

At Week 24, subjects who have not achieved at least 20% improvement from Day 1 in both swollen joint count (SJC) and tender joint count (TJC) will discontinue investigational study drug dosing but will continue with study visits and assessments per protocol. All subjects meeting this criterion who discontinue from investigational therapy are to receive standard of care treatment for their RA as determined by the investigator.

All subjects who attain responder status at Week 24 will continue on their assigned study drug, in a blinded fashion through Week 52. Placebo-responders at Week 24 will continue on placebo in a blinded fashion through Week 52.

All subjects who have received at least one dose of study drug and exit the study early will complete an early termination (ET) visit at the time of study discontinuation, with a follow up visit four weeks after the last dose of study drug (Post Treatment visit Week 4), regardless of dosing duration.

At completion of the 52-week dosing period all subjects (who did not discontinue assigned study drug or have not met criteria for loss of therapeutic response) will be provided the option to enroll into a separate Long Term Extension (LTE) study (GS-US-417-0304).

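### SAP 6.1 sets aside later data from subjects kept on drug after failing the Week 24 check, but has no matching rule for subjects kept on drug after confirmed loss of response, so late results up to Week 52 depend partly on site compliance

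*SAP*

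**What the plan says.** Protocol 3.2 has two response-based stops. At Week 24, "subjects who have not achieved a 20% improvement from Day 1 in both SJC and TJC will discontinue investigational therapy". Later, "All subjects will be evaluated for loss of therapeutic response from Week 30 through the Week 52 study visit", and "Subjects failing to maintain at least a 20% improvement from Day 1 in TJC and SJC (as confirmed at 2 consecutive visits) will discontinue" drug while remaining in study visits. The synopsis and the footnotes to the study procedures table (Appendix 2) repeat both.

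SAP 1.2 describes the Week 24 stop and continues: "All subjects who attain responder status at Week 24 will continue on their assigned study drug, in a blinded fashion through Week 52". The later stop appears there only indirectly, in the sentence on eligibility for the extension study, and its criteria are not given.

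SAP 6.1 builds the primary dataset from on-treatment data, which SAP 3.8.2 ends 7 days after the last dose of any study drug. It then adds an exclusion: "For subjects who continued study drug BUT did not achieve at least 20% improvement from Baseline in both SJC66 and TJC68 at" the nominal Week 24 visit, later efficacy data are dropped. If Week 24 status is missing, the check moves to Week 30 and "efficacy data collected after nominal Week 30 visit will be excluded from the primary analysis". If both statuses are missing, everything is kept. SAP 6.5, which lists changes from the protocol's efficacy analyses, does not mention this rule.

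**The concern.** SAP 6.1 anticipates that some subjects will stay on drug after they should have stopped, and does not let their later data count. It applies that principle to one of the protocol's two response-based stops and gives no reason for leaving out the other.

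For confirmed loss of response, the only remaining cut is last dose plus 7 days. That follows the stop that happened, not the stop the protocol required. What a subject contributes at Week 52 then depends on what the site did as well as on how the subject fared. The endpoints exposed are the late ACR20/50/70 and DAS28(CRP) response rates, the late continuous measures, Week 52 mTSS (named in a secondary objective) and the Week 52 no-progression proportion.

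**Working it through.** **1. The plan's own figures.** The documents give no rate of confirmed loss and no rate of continued dosing after it. The design figures do reproduce. For mTSS, n per arm = 2 × (1.960 + 1.282)² × 2.7² / 0.62² = 399, against 400 stated; 400 per arm gives 90.1% power. For ACR20, 78% of 200 against 62% of 400 gives 98.3% power, in line with the stated value of over 90%. All are Week 24 quantities and this point changes none of them.

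**2. The rules side by side.**

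| Situation | Protocol 3.2 | SAP 6.1, subject still on drug |
|---|---|---|
| Fails at Week 24 | Stop | Data after Week 24 excluded |
| Week 24 status missing, fails at Week 30 | No explicit rule for a missing Week 24 status; loss of response needs two consecutive visits | Data after Week 30 excluded |
| Passes Week 24, fails Weeks 30 and 36 | Stop | No exclusion |
| Passes Week 24, fails Weeks 36 and 44 | Stop | No exclusion |
| Week 24 and Week 30 both missing, fails Weeks 36 and 44 | Two consecutive failing visits | No exclusion |

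A pair completed at Week 52 leaves no later data. The exposed results are therefore those at Week 44 (after a Week 30/36 pair) and at Week 52 (after either pair).

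**3. Two subjects with the same joint counts.** Both pass Week 24 and fail at Weeks 30 and 36.
- Subject A is stopped at Week 36. Week 52 data fall outside the on-treatment period. Under NRI (SAP 6.1) A is a non-responder. In the mixed model for repeated measures (MMRM, SAP 6.4.2) A's Week 52 value is missing. A also drops out of the no-progression analysis, which uses observed cases.
- Subject B is left on drug. B's Week 52 values are observed and used, and B may count as a responder.

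**4. Other analyses.** The per-protocol set (SAP 3.1.3) considers deviations only up to Week 24. The all-available-data summary (end of SAP 6.4.2) treats A and B alike but has no formal testing.

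**5. Size, with assumed inputs.** Let f be the share of an arm with confirmed loss, q the share of those left on drug, and r the share of those who are responders at Week 52. Compared with full compliance, the arm's Week 52 rate moves by 100 × f × q × r points. All three inputs are assumptions: f 3–15%, q 10–100%, r 20–40%.

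| f | q | r | Points | Subjects per 400 |
|---|---|---|---|---|
| 3% | 10% | 20% | 0.06 | 0.2 |
| 5% | 30% | 40% | 0.6 | 2.4 |
| 10% | 50% | 40% | 2.0 | 8 |
| 15% | 100% | 40% | 6.0 | 24 |

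**6. Treatment difference.** With equal f, q and r in two arms the shifts cancel. If f is 15% on MTX alone and 5% on a filgotinib arm, with r = 30%, the difference moves by 100 × (0.15 − 0.05) × q × 0.30. That is 0.3, 1.5 or 3.0 points at q = 10%, 50% or 100%, in this example towards a smaller difference.

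**7. With the matching exclusion.** A and B are both non-responders at Week 52, so this dependence on compliance is 0 points for NRI endpoints. In MMRM both are missing after the confirming visit.

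**The case against.** The case for leaving the text alone has four parts.

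- **Limited reach.** Week 52 endpoints are other secondary, outside the testing hierarchy, with nominal p-values. The effect also needs sites to keep dosing against the protocol, and nothing in the documents says how often that would happen. This stands, and it limits the importance of the point.
- **An on-treatment strategy may use whatever is observed on drug.** That would be coherent if applied throughout. SAP 6.1 does not apply it to Week 24 failures, so it does not explain the different handling of the second stop.
- **SAP 1.2 is only a summary.** Its sentence on Week 24 responders closely follows one in Protocol 3.2, and SAP 1.2 does allude to loss of response. This stands as far as it goes, but the stop itself is not stated in the SAP.
- **The protocol's rule is not consistently worded.** Protocol 3.5.2 lists "Non-responder at Week 14 OR at 2 consecutive visits after Week 30 as outlined in Section 3.2", whereas Section 3.2 has Week 24 for the first stop and begins the second from Week 30. Whether Week 30 can be the first failing visit is therefore unclear. This stands and must be settled before any rule is programmed.

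A reader might also infer that the Week 30 cut contradicts the protocol, because it acts on one failing visit where loss of response needs two. The documents do not support going that far. The cut applies only when Week 24 status is missing and stands in for a check that is itself made at a single visit. The protocol does not say how such a subject is classified, and its later rule speaks of failing to maintain an improvement. The cut's reach is also small: if 1–5% of 1200 subjects had no Week 24 status and 10–20% of those failed at Week 30 (assumed), it would touch 1200 × 0.01 × 0.10 = 1.2 to 1200 × 0.05 × 0.20 = 12 subjects.

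**Conclusion.** The gap is real: the primary dataset handles continued dosing after one protocol stop and says nothing about the other. Late results, up to Week 52, therefore depend partly on whether sites stopped drug when required.

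The size cannot be established from the documents. The range of 0.06 to 6.0 points on an arm's rate rests entirely on assumed f, q and r. Its upper end needs every subject with confirmed loss to have been left on drug, so it should not be read as an expected effect.

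Nor should a reader infer that the primary result or the control of type I error is at stake. The Week 24 ACR20 and DAS28(CRP) tests use no data that this rule touches. The one caveat concerns the Week 24 MMRM estimates: SAP 6.3.2 includes all available postbaseline visits, so if later visits enter the model those estimates could move slightly.

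This is an inexpensive correction worth making before the Week 52 data are analysed.

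**What to change.** - **SAP 6.1:** add that, for subjects who continued study drug after meeting the protocol's confirmed loss-of-response criterion, efficacy data after the confirming visit are excluded from the primary dataset.
- **SAP 1.2:** state both protocol stops.
- **Before programming:** the sponsor should reconcile Protocol 3.2 with Protocol 3.5.2, on Week 14 against Week 24 and on from Week 30 against after Week 30. The Week 30 cut in SAP 6.1 need not be replaced, but it should be reconciled with the protocol, with a sentence saying how a missing Week 24 status is treated.

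This concerns analysis handling only; which clinical rule is right is for the sponsor to settle.

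The cost is SAP wording and one derivation from joint counts already collected. Sample size, power and alpha do not change. The downside is that a few subjects' observed late on-drug data leave the primary dataset; they remain in the all-available-data summary.

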#### **Selection of Efficacy Data in the Event of Multiple Records in an Analysis Visit Window**

If multiple valid and nonmissing efficacy measurements exist in an analysis window, then records will be chosen based on the following rules if a single value is needed:

- The record closest to the nominal day for that visit will be selected
- If there are 2 records that are equidistant from the nominal day, or more than 1 record (with time known) on the selected day, the latest record will be taken
- If chronological order cannot be determined (eg, more than 1 record on the same day with time missing), for any given subject, the worst outcome will be selected.

For the calculation of composite endpoints including DAS28(CRP), ACR20/50/70, ACR-N, SDAI, and CDAI, we use the following steps unless otherwise specified:

- Step 1: Assign individual components to analysis visit windows defined in Section 3.8.2
- Step 2: Within each analysis visit window, select the component-level data based on the rules for selecting efficacy data as above
- Step 3: Calculate the composite endpoint based on the selected component-level data in Step 2.

## **Missing Data Imputation**

Below are the descriptions for the imputation methods that will be used throughout the efficacy analyses:

- Observed case (OC): Missing values remain missing. For the categorical composite endpoints, in the case that some components are missing, the composite endpoint assessment will be derived based on the non-missing components. If non-missing components are not sufficient to determine final composite endpoint, then the composite endpoint will be set as missing. For continuous composite endpoints (including ACR-N), if any components are missing, the composite endpoints will be set as missing.
- Last observation carried forward (LOCF): Baseline measurements will not be carried forward to postbaseline. Only postbaseline measurements will be LOCF. For the composite endpoints, the last nonmissing postbaseline observation will be carried forward to subsequent visits for each individual component, and then calculate the composite endpoints using individual components imputed by LOCF as described above. If a subject does not have a nonmissing observed record for a postbaseline visit, the last postbaseline record prior to the missed visit will be used for this postbaseline visit. If the last nonmissing observation prior to the missing visits cannot be determined due to multiple measurements occurring at the same time or the time not available within the same day, the worst outcome will be used for LOCF. If missing components still exist after LOCF, the composite endpoints will be calculated using the same rules as described in OC.
- Non-responder imputation (NRI): For all binary response measurements, starting from OC, all missings will be set as non-responders.

If subject only had baseline measurements, LOCF and OC analyses will not include this subject. But this subject will be treated as non-responder in NRI analyses.

### **6.1.1. Tender/Swollen Joint Counts (TJC/SJC)**

The TJC68 and SJC66 will be collected during the course of the study. The assessment for each joint will be from the following selections: Tender Only, Swollen Only, Tender and Swollen, Joint Non-Evaluable or Missing, or Not Tender or Swollen.

Individual joint with missing assessment will not be imputed. If at least half of the joints are assessed at a given visit, the prorated tender and swollen joint counts will be calculated using the following formula:

$$\text{TJC68} = \frac{\text{Total number of tender joints}}{68 - (\text{Number of nonevaluable or missing joints out of 68 joints})} \times 68$$
$$\text{SJC66} = \frac{\text{Total number of swollen joints}}{66 - (\text{Number of nonevaluable or missing joints out of 66 joints})} \times 66$$

If less than half of joints are assessed at a given visit, joint counts are treated as missing for that visit.

A more abbreviated assessment considering 28 joints as listed in [Table 6-1](#) for both tenderness and swelling will also be conducted (as part of the TJC68 and SJC66 assessment), denoted as TJC28 and SJC28, respectively.

**Table 6-1. Composition of the 28 Joints**

Joints	Number
Shoulder Joints (Left and Right)	2
Elbow Joints (Left and Right)	2
Wrist Joints (Left and Right)	2
Metacarpophalangeal Joints I-V (Left and Right)	10
Proximal Interphalangeal Joints I-V (Left and Right) – Hands only	10
Knee Joints (Left and Right)	2

If there exist non-evaluable or missing joints among the 28 joints, similar prorated tender and swollen joint counts will be calculated as follows:

$$TJC28 = \frac{\text{Total number of tender joints}}{28 - (\text{Number of nonevaluable or missing joints out of 28 joints})} \times 28$$

$$SJC28 = \frac{\text{Total number of swollen joints}}{28 - (\text{Number of nonevaluable or missing joints out of 28 joints})} \times 28$$

If less than half of the 28 joints are assessed at a given visit, TJC28 and SJC28 are treated as missing for that visit.

### 6.1.2. Global Assessment of Disease Activity

Subject’s Global Assessment of Disease Activity (SGA) and Physician’s Global Assessment of Disease Activity (PGA) based on a 0-100 visual analog scale (VAS) will be recorded during the study, with 0 indicating “no disease activity” and 100 indicating “maximum disease activity” (or similar description of disease severity).

